10.4.3 Handling of missing values/censoring/discontinuations

PFS times will be censored if no PFS event is observed before the cut-off date. The censoring date will be the date of last adequate tumor assessment before the cut-off date. If a PFS event is observed after two or more missing or non-adequate tumor assessments, then PFS will be censored at the last adequate tumor assessment. If a PFS event is observed after a single missing or non-adequate tumor assessment, the actual date of event will be used (see RECIST 1.1. [Appendix 3](#)). It is not intended to censor patients for new anticancer therapy prior to documented disease progression in the primary analysis.

10.4.4 Supportive and sensitivity analyses

The following analyses of PFS will be performed in the *PIK3CA* mutant cohort to support the primary PFS analysis, where the primary endpoint is statistically significant.

A sensitivity analysis to support the primary PFS analysis will be conducted where patient's PFS times are censored at the onset of new anticancer therapy.

Subgroup analyses of PFS may be performed in the *PIK3CA* mutant cohort (if the primary endpoint is statistically significant) based on each level of the stratification factors and other prognostic baseline demographic or disease characteristic factors listed below:

- Age
- Race
- ECOG performance status at baseline
- Measurable vs. non-measurable lesions at baseline
- Previous treatment with endocrine therapy for metastatic disease

Additional baseline disease characteristic factors that are deemed relevant may be specified in the SAP. The analyses for the subgroups will include hazard ratios (together with associated two-sided 95% confidence intervals) from un-stratified Cox proportional hazards models.

In addition, the analysis of PFS using stratified Cox proportional hazards model may be repeated using the PPS in the cohort where the primary endpoint is statistically significant.

PFS events will be described according to the type of events (death, documented progression) by treatment arm in the FAS. Censoring reasons will be described by treatment arm. A sensitivity analysis to support the primary PFS analysis will be conducted where patient's PFS times are censored at the onset of new anticancer therapy.

PFS assessed by BIRC will serve as supportive evidence of the primary endpoint. A sample based BIRC audit strategy will be used to assess PFS by BIRC. Two methods will be used to summarize the data from the sample-based BIRC assessment in the PIK3CA mutant cohort. The NCI (National Cancer Institute) method (Dodd et al 2011), uses an auxiliary variable estimator of the log-hazard ratio that combines information from patient-level investigator assessment from all patients in the PIK3CA mutant cohort and the BIRC assessment of these patients randomly selected for central review. This estimate and its one-sided 95% CI will be provided. Details of the audit sample size calculation for the BIRC assessment are provided in Section 10.8. The NCI method will be used for audit sample size determination and summary of treatment effect (HR, 95% confidence intervals) based on the supportive BIRC assessment.

The data from the BIRC assessment generated following the sampling scheme as above will also be summarized using the method proposed by Amit et al 2011, referred to as the PhRMA (Pharmaceutical Research and Manufacturers in America) method. With this approach, the differential discordance (DD) of the early discrepancy rate (EDR) and late discrepancy rate (LDR) between the two arms will be estimated as the rate on the alpelisib+fulvestrant arm minus the rate on the placebo+fulvestrant arm. The EDR and LDR results will also be summarized by treatment arm. Further definitions and details will be provided in the statistical analysis plan.

10.5 Secondary objectives

All secondary efficacy analyses will be reported for each cohort by treatment arm where appropriate. Analyses will be based on the FAS unless otherwise specified.

10.5.1 Key secondary objective(s)

The key secondary objective of the study is to determine whether treatment with alpelisib in combination with fulvestrant prolongs OS compared to treatment with placebo for the cohort of patients with *PIK3CA* mutant status.

OS is defined as the time from date of randomization to date of death due to any cause. If a patient is not known to have died, then OS will be censored at the date of last known date patient alive.

In the *PIK3CA* mutant cohort, a hierarchical testing procedure will be adopted and the OS analyses will be performed only if the primary efficacy endpoint PFS is statistically significant.

Assuming proportional hazards model for OS, the following statistical hypothesis for OS will be tested using a stratified log-rank test (according to randomization stratification factors) at the one-sided 2.0% level of significance :

$$H_0: \theta_2 \geq 0 \text{ vs. } H_a: \theta_2 < 0$$

where θ_2 is the log-hazard ratio (alpelisib-fulvestrant treatment arm vs. placebo-fulvestrant treatment arm) of OS.

The analysis for OS will be based on the FAS population according to the treatment arm patients were randomized to and the strata they were assigned to at randomization.

The final OS analysis will not be performed at the time point of the final PFS analysis in the *PIK3CA* mutant cohort, but after additional follow-up. Therefore, a three-look group sequential design is considered for OS.

OS will be hierarchically tested for the *PIK3CA* mutant cohort in the following way:

- The first potential timepoint for OS analysis will be at the time of the PFS efficacy interim analysis after approximately 37% of the expected deaths are observed, at which point approximately 66 deaths are expected. If PFS is not statistically significant at this stage, then OS will not be tested, in which case the next potential timepoint for OS analysis will be at the time of the final PFS analysis after approximately 57% of the expected deaths are observed, at which point approximately 101 deaths are expected to have been recorded in the clinical database.
- If OS is not statistically significant at the first interim analysis, the 2nd OS analysis will be planned after approximately 85% of the expected deaths are observed, at which point approximately 151 deaths have been recorded in the clinical database.
- If OS is not statistically significant at this stage, a final analysis is planned at the time approximately 178 deaths have been recorded.
- If PFS is not statistically significant at the final analysis for PFS, then OS will not be tested.

The type I error probability will be controlled by using a separate Lan-DeMets (O'Brien-Fleming) alpha spending function independent of the Haybittle-Peto boundary used for the primary efficacy analysis of PFS at a 2.0% level of significance for the *PIK3CA* mutant cohort. This guarantees the protection of the overall type I error ($\alpha = 2.5\%$) across all hypotheses and the repeated testing of the OS hypotheses at the interim and the final analyses (Glimm 2010). This includes hypotheses associated with the secondary endpoints PFS and OS in the *PIK3CA* non-mutant cohort (PFS in the non-mutant cohort will be tested at a 0.5% level of significance if PoC is established).

OS will be estimated using the Kaplan-Meier method. The median OS along with 95% confidence intervals will be presented by treatment arm. Stratified Cox regression will be used to estimate the HR of OS, along with 95% confidence interval.

10.5.2 Other secondary efficacy objectives

Analyses will be based on the FAS.

10.5.2.1 PFS in patients with *PIK3CA* non-mutant status measured in tissue

PFS in the *PIK3CA* non-mutant cohort will be analyzed at a single look based on the FAS population according to the treatment arm patients were randomized to and the strata they were assigned to at randomization.

PFS treatment effect in this cohort will be considered to be clinically relevant via a Bayesian decision rule if:

- The estimated HR (stratified according to presence of lung and/or liver metastasis and previous treatment with CDK4/6 inhibitor) ≤ 0.60

and

- The posterior probability ($HR < 1$) $\geq 90\%$

The posterior probability in the second criterion will be derived from the Bayesian posterior distribution of the HR. Assuming a non-informative prior distribution, the distribution of the HR will be updated with all available data from the patients included in the FAS in this cohort. The cumulative posterior distribution will be used to derive the probability that the true HR is less than 1.

If both these criteria are met then the comparison of PFS between the two treatment arms in this cohort using a stratified log-rank test at a one-sided 0.5% level of significance, will be made. Assuming proportional hazards model for PFS, the following statistical hypotheses will be tested at the one-sided 0.5% level of significance:

$$H_{01}: \theta_1 \geq 0 \text{ vs. } H_{a1}: \theta_1 < 0$$

where θ_1 is the log-hazard ratio (alpelisib + fulvestrant treatment arm vs. placebo+fulvestrant treatment arm) of PFS.

The median PFS along with 95% confidence intervals will be presented by treatment arm.

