14.6.2.1 Bayesian methodology for proof of concept criteria

Let θ denote the natural logarithm of the hazard ratio (HR) of PFS (experimental arm vs. control, i.e. $\theta < 0$ indicates efficacy in favor of the experimental arm i.e. alpelisib + fulvestrant) and y_m denote the log(HR) estimated from a Cox proportional Hazards model with treatment as covariate based on m observed events and then using asymptotic theory of the log hazard ratio ([Schoenfeld 1981](#)):

$$Y_m \sim N(\theta, 4/m)$$

Further assume θ follows a conjugate normal prior distribution, written as

$$\theta \sim N(\theta_0, 4/n_0)$$

where θ_0 is the specified prior mean and the prior variance $4/n_0$, n_0 is the number of events worth of prior information.

This results in a posterior distribution of θ as

$$\theta | y_m \sim N(\phi y_m + (1 - \phi) \theta_0, 4/(m+n_0))$$

where $\phi = m/(m+n_0)$ and in this study we consider a non-informative prior with $n_0=0$.

Therefore the posterior distribution is of the following form;

$$\theta | y_m \sim N(y_m, 4/m)$$

The cumulative posterior distribution will be used to derive the probability that the true HR is less than 1.

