14.6.2.2 Proof of concept (PoC) criteria

The following PoC criteria, based on analysis of PFS using Cox proportional Hazards model with treatment as covariate, are considered;

- Estimated HR ≤ 0.6 , and
- Posterior Probability (HR < 1) $\geq 90\%$

Both criteria need to be met in order to meet primary objective for this part of the study and test PFS in this cohort using a stratified log-rank test at one-sided 0.5% level of significance. The first criterion is met if the estimated HR is 0.6 or less which is the minimum HR of clinical interest. The second criterion provides reasonable evidence that the estimated HR is better than the value of no interest (HR=1) and also guarantees a level of precision for the estimate of HR.

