14.6.2.2.1 Sample size considerations and simulation details

Based on the assumption that log (HR) is normally distributed, then the minimum number of events to satisfy criterion (b) can be calculated ([Schoenfeld 1981](#)) as:

$$\# \text{ events} = 4 (z_{1-\alpha} + Z_{1-\beta})^2 / \theta^2$$

Taking, $\theta = \log(0.6)$, and one-sided, $\alpha=0.005$, $\beta=0.5$, then 102 events are required. That is, with at least 102 events if the estimated HR is < 0.6 then criterion (b) in [Section 14.6.2.2](#) will be met.

Assuming an enrollment rate of 10 patients during the first 6 months (7 with *PIK3CA* non-mutant status), 30 patients up to 12 months (21 with *PIK3CA* non-mutant status) and 50 patients afterwards (35 with *PIK3CA* non-mutant status) and 10% patients will be lost to follow-up, 220 patients will be randomized (110 per arm), in order to observe the required 102 events in the two arms in approximately 18 months (if the observed HR is 0.6 and the median PFS for the control arm is 7.4 months).

The primary analysis to estimate the HR will be performed after approximately 102 PFS events have been observed. If the true HR is 1, the probability (obtained by simulation) to obtain a positive conclusion is 0.005. If the true HR is 0.60 (reflecting the minimum clinically relevant difference), the probability to meet efficacy criteria is 0.491. In addition if the true HR is 0.6 and the PoC is met, the probability (by simulation) to also observe a positive result with formal testing is 0.983.

Table 14-12 Operating characteristics for PoC criteria in PIK3CA non-mutant cohort

True HR	True Median PFS alpelisib (months)	Probability to meet PoC
0.3	24.67	0.999
0.4	18.50	0.975
0.5	14.80	0.813
0.6	12.33	0.491
0.7	10.57	0.220
0.8	9.25	0.076
0.9	8.22	0.020
1.0	7.4	0.005

Assumes: (1) HR.=0.6, (2) true median PFS for fulvestrant = 7.4 months, (3) protocol planned accrual

*Probabilities conditional on PoC criteria being met. Formal testing using log-rank test at a one-sided

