3.8.1.4 Hazard Ratio

The PFS hazard ratio with two-sided 95% confidence interval will be derived from the stratified Cox proportional hazards model for each cohort. In this analysis the baseline hazard function will be allowed to vary across strata. SAS PHREG procedure with ties=EXACT option will be used to carry out this analysis in which the model statement will include treatment arm variable as the only covariate and the STRATA statement will include the stratum information as obtained via IRT.

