4.4.4 Hazard ratio

The hazard ratio as a measure of treatment effect will be derived from the Cox proportional hazards model using SAS procedure PHREG with TIES=EXACT option in the MODEL statement. The stratified unadjusted Cox model will be used (where the baseline hazard function is allowed to vary across strata) for the primary analysis, i.e. the MODEL statement will include only the treatment arm variable as a covariate and the STRATA statement will include stratification variable(s). The strata information will be based on the data obtained from IRT that was utilized for randomization.

General SAS code for the stratified Cox model

```
PROC PHREG data=dataset;
  MODEL survtime*censor(1)=trt / TIES=EXACT;
  STRATA stratum 1 stratum 2;
  RUN;

/* survtime represents variable containing event/censor times;
censor represents censoring variable (1=censored, 0=event);
trt represents treatment arm variable;
stratum 1 and stratum 2 represent IRT stratification variables */
```

Hazard ratio with two-sided 95% confidence interval will be based on Wald test.

Note: Ideally, the hazard ratio and the confidence interval should be derived by a method consistent with the p-value calculation, i.e. in this case with log-rank test. This requirement would lead to the score test based intervals. However, score test-based confidence intervals are not available in SAS procedure PHREG therefore Wald test based intervals will be used instead.

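### Is the non-mutant proof-of-concept gate defined on two different hazard ratios, with a posterior criterion that adds nothing?

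*Protocol*

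**What the plan says.** Protocol 10.5.2.1 and SAP 3.8.2.2 set the gate. Criterion (a) is a hazard ratio of at most 0.60, and the text specifies which one: "The estimated HR (stratified according to presence of lung and/or liver metastasis and previous treatment with CDK4/6 inhibitor". Criterion (b) is a posterior probability of at least 90% that the hazard ratio is below 1. If both are met, PFS is tested with a stratified log-rank test at one-sided 0.5%. OS in this cohort depends on the same gate (Protocol 10.5.2.2, SAP 3.8.2.3).

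Protocol 14.6.2.1 defines the log hazard ratio that feeds the posterior as "estimated from a Cox proportional Hazards model with treatment as covariate based on" m events, with variance 4/m and a flat prior. Protocol 14.6.2.2 then says that both criteria are "based on analysis of PFS using Cox proportional Hazards model with treatment as covariate". SAP 4.7.1 and 4.7.2 repeat this. None of the four sections mentions strata for the Cox model.

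On the event count, Protocol 14.6.2.2.1 says that "the minimum number of events to satisfy criterion (b) can be calculated", and obtains 102 with one-sided alpha 0.005 and beta 0.5. Protocol 14.6.2.2 also says that the second criterion "guarantees a level of precision for the estimate of HR".

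**The concern.** Two things look wrong.

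First, a sharp cut at 0.60 decides whether non-mutant PFS, and then OS, is formally tested at all. If one section means a stratified estimate and another an unstratified one, a result close to 0.60 could pass under one and fail under the other, and the choice could be made after seeing the data.

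Second, the 102 events are attributed to a 90% posterior criterion but computed with the z-value of a 0.5% test. If criterion (b) is always met when (a) is, the dual criterion is in effect a single one, and the claimed precision safeguard does no work.

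**Working it through.** **Inputs.** Threshold hazard ratio 0.60, posterior N(y_m, 4/m), one-sided alpha 0.005, beta 0.5 and 102 events (Protocol 14.6.2); 220 patients, 1:1 (Protocol 10.8); ln(0.6) = −0.5108.

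**1. The plan's own figure.** Events = 4(z_{1−α} + z_{1−β})² / ln(0.6)². With z = 2.576 and z_{0.5} = 0, this is 4 × 2.576² / 0.5108² = 101.7, so 102. The figure reproduces, but from the 0.5% test.

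**2. Events needed for criterion (b).** With z_{0.90} = 1.2816: 4 × 1.2816² / 0.5108² = 25.2, so 26. The label in Protocol 14.6.2.2.1 and SAP 4.7.3 is therefore wrong.

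**3. Criterion (b) at 102 events.** The standard error is 2/√102 = 0.198.
- At an estimated hazard ratio of 0.60, the posterior is Φ(0.5108 / 0.198) = 0.995.
- The hazard ratio that just gives 90% is exp(−1.2816 × 0.198) = 0.776.
- The hazard ratio that just gives one-sided p = 0.005 is exp(−2.576 × 0.198) = 0.6004.

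So (a) implies (b) at the planned count. For (b) to bind at 0.60, the standard error would have to be 0.399, about 2.01 times the planned value. With fewer than 26 events it would bind: at 25 events the posterior at 0.60 is 0.899.

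**4. Do the published pass probabilities depend on (b)?** Using (a) alone, P(pass) = Φ((ln 0.6 − ln HR) / 0.198):

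| True HR | (a) alone | Protocol Table 10-5 |
|---|---|---|
| 0.3 | 0.9998 | 0.999 |
| 0.4 | 0.980 | 0.975 |
| 0.5 | 0.821 | 0.813 |
| 0.6 | 0.500 | 0.491 |
| 0.7 | 0.218 | 0.220 |
| 0.8 | 0.073 | 0.076 |
| 0.9 | 0.020 | 0.020 |
| 1.0 | 0.0049 | 0.005 |

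All agree within one percentage point, and adding (b) changes none of them.

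**5. Stratified or not: the texts side by side.**
- The sections that state the decision rule (Protocol 10.5.2.1, SAP 3.8.2.2) say stratified. The OS gate in Protocol 10.5.2.2 and SAP 3.8.2.3 refers back to those sections.
- SAP 3.8.1.4 says the PFS hazard ratio "will be derived from the stratified Cox proportional hazards model for each cohort".
- SAP 4.4.4 shows what treatment as covariate means in this SAP's stratified model: "the MODEL statement will include only the treatment arm variable as a covariate and the STRATA statement will include stratification variable(s".
- Where an unstratified model is intended, the documents say so: the subgroup models in Protocol 10.4.4 and the sensitivity analysis in SAP 3.8.1.5.

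The appendix wording therefore fits the stratified model. It omits a word and does not define a second estimator.

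**6. Size of the effect if someone did fit an unstratified model.** Simulation with 220 patients, 102 events and 4,000 trials per row (8,000 at HR 1). Assumed, because the documents give no figures: half the patients in one lung/liver stratum, 10% with prior CDK4/6 treatment, and either no strata effect or a hazard ratio of about 2 between lung/liver strata (with 1.4 for CDK4/6).

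| True HR | Strata effect | Stratified ≤ 0.60 | Unstratified ≤ 0.60 | Opposite sides |
|---|---|---|---|---|
| 0.6 | none | 0.494 | 0.491 | 4.2% |
| 0.6 | strong | 0.488 | 0.447 | 7.0% |
| 0.7 | none | 0.223 | 0.219 | 3.3% |
| 0.7 | strong | 0.225 | 0.195 | 5.3% |
| 1.0 | none | 0.006 | 0.006 | 0.1% |
| 1.0 | strong | 0.006 | 0.004 | 0.3% |

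Under a mixed reading, with (a) stratified and (b) from an unstratified model, no simulated trial met (a) and failed (b). The lowest posterior was 0.957.

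**The case for a change.** The strongest case for a change is that a gatekeeping rule should not rest on inference. Protocol 14.6.2.2 uses the word stratified for the log-rank test and leaves it out for the Cox model a few lines earlier. SAP 3.8.1.4 sits in the primary-endpoint section, SAP 4.4.4 states its convention for the primary analysis, and the proof-of-concept sections refer to neither. The appendix is also not fully aligned with the body elsewhere: it assumes accrual of 10, 30 and 50 patients where Protocol 10.8 has 12, 35 and 59. A disagreement of 3% to 7% near the threshold is not negligible for a yes/no decision.

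Part of this stands. The 102 is mislabelled, the precision sentence credits criterion (b) with what the event count provides, and the missing word would have been better included.

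The rest does not carry through. The decision rule sits in sections that do say stratified, and SAP 3.8.1.4 extends the stratified model to each cohort, so an analyst is not left to choose. The 3% to 7% rests on assumed strata and would arise only if those sections were disregarded. Even then, an unstratified pass with a stratified hazard ratio above 0.60 would generally fail the stratified test that follows, whose critical value is about 0.6004. The redundancy of (b) is not hidden either: Protocol 14.6.2.2.1 and SAP 4.7.3 both say that with at least 102 events an estimate below 0.6 meets it.

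**Conclusion.** No change to the plan is needed. The arithmetic criticism is correct but clerical: 102 is the count at which a hazard ratio of 0.60 reaches one-sided p = 0.005, and the 90% criterion would need 26. At 102 events criterion (b) is slack (0.995 against 0.90). It remains a harmless backstop that would bind at 0.60 only below 26 events under the 4/m variance. The claim of two hazard ratios is not borne out: the gate is stated as stratified, and the appendices leave out a word that the SAP's own conventions supply.

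Followed as written, the plan gives the same 102 events, 220 patients, proof-of-concept probabilities and gate decision. Type I error is not inflated, because the one-sided 0.5% stratified log-rank test still follows the gate. Relabelling the count and adding the word would tidy the text without altering any result. This conclusion rests on the normal approximation with variance 4/m that the plan itself adopts, and on analysts following the sections that state the decision rule.

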10.5.2.2 OS in patients with *PIK3CA* non-mutant status measured in tissue

OS analyses will be performed only if the secondary efficacy endpoint, PFS, in this cohort meets the PoC criteria given in [Section 10.5.2.1](#) and is statistically significant. A hierarchical testing procedure will be adopted. Assuming proportional hazards model for OS, the following statistical hypotheses will be tested at the one-sided 0.5% level of significance:

$$H_{01}: \theta_1 \geq 0 \text{ vs. } H_{a1}: \theta_1 < 0$$

where θ_1 is the log-hazard ratio (alpelisib + fulvestrant treatment arm vs. placebo+fulvestrant treatment arm) of OS.

The analysis for OS will be based on the FAS population according to the treatment arm patients were randomized to and the strata they were assigned to at randomization.

The final OS analysis will not be performed at the time point of the final PFS analysis in the *PIK3CA* non-mutant cohort, but after additional follow-up. Therefore, a three-look group sequential design is considered for OS.

If PFS in the non-mutant cohort meets the PoC criteria and is statistically significant at a one-sided 0.5% level of significance, OS will be hierarchically tested in the following way:

- The first timepoint for OS analysis will be at the time of the final analysis for PFS (provided PFS is statistically significant) when approximately 29% of the expected deaths are observed, at which point approximately 36 deaths in the *PIK3CA* non-mutant cohort have been recorded (after approximately 18 months from the first patient to be randomized in this cohort).

- If OS is not statistically significant at the first interim analysis, the 2nd OS analysis will be planned after approximately 87% of the expected deaths are observed, at which point approximately 109 deaths are expected to have been recorded in the clinical database.
- If OS is not statistically significant at the second interim analysis, a final analysis is planned after approximately 125 deaths are expected to have been recorded in the clinical database.
- If PFS is not statistically significant, then OS will not be tested.

OS will be estimated using the Kaplan-Meier method. The median OS along with 95% confidence intervals will be presented by treatment arm. Stratified Cox regression will be used to estimate the HR of OS, along with 95% confidence interval.

